10.1.3. Events that Require Expedited Reporting to Sponsor

The following events also require reporting to the sponsor (or designee) within 24 hours of learning of the event.

- SAEs.
- Selected Adverse Events of Special Interest (AESI; serious and nonserious): Adverse events of special interest for this study include the following:
 - Hypoglycemia, defined as blood glucose <54 mg/dL, regardless of symptoms.
 - NODM

For patients with no diabetes at baseline:

a. Two values of fasting (≥8 hours) plasma glucose ≥126 mg/dL (7.0 mmol) during the treatment period

OR

b. Two values of HbA1c ≥6.5% (48 mmol/mol) during the treatment period

Patients who meet either of these criteria during the placebo run-in period will be considered to have diabetes at baseline.

- Hyperglycemia requiring treatment, defined as:
- a. HbA1c ≥10.5% AND increase in HbA1c of ≥1.5% from baseline value OR
- b. Fasting glucose ≥250 mg/dL on 2 occasions including symptoms consistent with hyperglycemia AND increase in fasting glucose >50 mg/dL above baseline
 - Development of new or worsening of autoimmune disease

- Moderate or severe hypersensitivity reactions
- Moderate or severe infusion reactions

Other Events that Require Accelerated Reporting to Sponsor

The following events also require reporting to the sponsor (or designee) within 24 hours of learning of the event:

- **Pregnancy:** Although pregnancy is not considered an AE, it is the responsibility of the investigator to report to the sponsor (or designee), within 24 hours of identification, any pregnancy occurring in a female or female partner of a male, during the study or within 16 weeks of the last dose of study drug. Any complication of pregnancy affecting a female study patient or female partner of a male study patient, and/or fetus and/or newborn that meets the SAE criteria must be reported as an SAE. Outcome for all pregnancies should be reported to the sponsor.
- **Symptomatic Overdose**: Accidental or intentional overdose of at least 2 times the intended dose of study drug within the intended therapeutic window, if associated with an AE.

For the AESIs based on a laboratory value, the AESI must be reported to Sponsor within 24 hours once the investigator confirms the abnormal laboratory value.

10.1.4. Other Adverse Events of Special Interest that Do Not Require Expedited Reporting to Sponsor

Although these AESIs do not require expedited reporting to the sponsor, the following events are of interest and will involve the collection of additional details in separate CRFs:

- Injection site reaction due to study treatment administration
- Mild infusion reactions due to study treatment administration
- Mild hypersensitivity reactions due to study treatment administration

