Patients with either moderate abnormalities of both HbA1c (>7.0%) and TG (>200 mg/dL), or a more severe abnormality of TG (>450 mg/dL), with normal or mildly abnormal HbA1c (up to 7.0%) are included. These inclusion criteria are met by the majority of FPLD patients and allow for separate analysis of REGN4461 treatment effects on each metabolic parameter.

The study includes adult patients only. Familial PLD is generally a progressive disease with pubertal onset of fat loss and a long delay between signs/symptoms and diagnosis. As such there is not a large population of pediatric patients with high unmet medical need.

Rationale for Study Endpoints:

The co-primary endpoints are the change in TG from baseline to week 12, and the change in HbA1c from baseline to week 12 in patients in cohort A. These co-primary endpoints were specifically selected because improvements in either or both parameters would help address the highest unmet medical need for PLD patients.

Significant heterogeneity in the response of fasting TG and HbA1c was observed in the metreleptin clinical trials. Given the uncertainty in treatment effect in FPLD patients and the limited number of FPLD patients, secondary endpoints include within-group analyses of all patients receiving their first 12 weeks of REGN4461. This includes individuals in study arm 1 (TP2) and study arm 2 (TP1). In addition, for Study Arm 1, the within group change for TP1 (placebo treatment) will be compared to TP2 (REGN4461 treatment).

The secondary endpoints also include analyses of fasting TG and HbA1c in the higher leptin cohort B. While data from Part B of REGN4461-HV-1794 suggest that a leptin level <8.0 ng/mL might identify individuals most likely to respond, some data suggest response to LEPR agonism in individuals with higher serum leptin, up to 20.0 ng/mL. Analyses of responses in cohort B will therefore allow for more accurate determination of a REGN4461-responsive patient population.

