- Initially, 2 measurements of leptin levels will be performed. If the 2 measurements are concordant (fall into the same leptin range: (i) less than 8.0 (ii) greater than or equal to 8.0 and less than or equal to 20.0 (iii) greater than 20.0 ng/mL) the measures will be sufficient to determine patient disposition; if they are discordant, a third measure will be obtained and the arithmetic average of the 3 measures will determine patient disposition. Patients will be assigned to a cohort based on the mean baseline leptin levels (<8.0 ng/mL [cohort A] or 8.0 to 20.0 ng/mL [cohort B]; Section 6.1.1).
- For those patients screened and found eligible under the original protocol, HbA1c and triglycerides assessments will be repeated to reconfirm eligibility of the patient if the screening window of 10 weeks has been exceeded by the time the relevant approvals for Protocol Amendment 1 are in place. Patients screened under the original protocol who do not enter the placebo run-in period within the prescribed visit window will not be considered screen failures, nor will they be considered a deviation provided repeat HbA1c and triglycerides are obtained prior to initiating the placebo run-in as part of Amendment 1. Note: patients who enter screening under the amendment will be

required to adhere to the 10-week screening schedule or it will be considered a deviation.

4-week single blind placebo run-in period (PBO); day -28 to day -1

All patients who meet eligibility criteria will receive placebo by IV infusion on day -28, followed by SC QW injections of placebo starting at day -21. Patients will be observed at least 4 hours after IV infusion to maintain study blinding. Fasting lipid and glucose levels will be collected weekly. Patients will receive training on electronic COA (eCOA) using a device to record COA measures such as hunger, pain, QoL, depression, and anxiety disorders. Patients will undergo baseline body composition by DXA and bioimpedance. Additionally, 2 baseline assessments of liver volume (MRI) and liver fat content (MRI-PDFF) will be performed; the first and second MRI must be performed on separate days.

12-week double-blind placebo-controlled treatment period (TP1); Day 1 until week 12

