8.2. Run-in Treatment

There will be a 4-week single-blind placebo run-in period (day -28 to day -1). At the beginning of the placebo run-in period, patients will receive an IV placebo infusion, followed 1 week later by SC QW injections of placebo, administered for 3 weeks.

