#### The AESIs include:

- Hypoglycemia, defined as blood glucose <54 mg/dL (eCRF, lab data)
- New onset diabetes mellitus (NODM) (eCRF, lab data)
- For patients with no diabetes at baseline, NODM is defined using the following lab parameters:
  - a. Two values of fasting ( $\geq 8$  hours) plasma glucose  $\geq 126$  mg/dL (7.0 mmol) during the treatment period

OR

- b. Two values of HbA1c ≥6.5% (48 mmol/mol) during the treatment period
- Hyperglycemia requiring treatment (eCRF, lab data), defined using the following lab parameter:
  - a. HbA1c ≥10.5% AND at the same visit an increase in HbA1c of ≥1.5% from baseline value

OR

- b. Fasting glucose ≥250 mg/dL on 2 occasions including symptoms consistent with hyperglycemia AND increase in fasting glucose >50 mg/dL above baseline
- Development of new or worsening of autoimmune disease (eCRF)
- Moderate or severe hypersensitivity reactions (CMQ, eCRF)
- Moderate or severe infusion reactions (eCRF)

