
 
Absolute change in HbA1c from baseline to week 12
 
Absolute change in HbA1c from week 12 to week 24
 
	
 
For Arm 1, baseline adjusted least-squares (LS) mean estimate at week 12 and week 12 adjusted least-squares (LS) mean estimate at week 24 will be provided along with the corresponding standard errors and 95% confidence intervals.
 
MMRM / Least-squares (LS) means with their corresponding standard errors and 95% confidence intervals.
 
Note: Treatment Group = Arm 1; Strata level = HbA1c>7.0%.
 
Note: Post baseline visits to include in the model are
 
	
 
For Arm 1, difference between the HbA1c mean changes from week 12 to week 24 and from baseline to week 12 will be provided along with its corresponding 95% confidence interval, and nominal p-value when appropriate.
 
REGN4461 in Arm 1 SBTP
 

Protocol: R4461-PLD-20100

	weeks 4, 6, 10, 12, 16, 18, 22, and 24.	versus Placebo Arm 1 DBTP

 
Change in fasting glucose from baseline to week 12
 
Change in fasting glucose from week 12 to week 24
 
	• For Arm 1, baseline adjusted least-squares (LS) means estimates at week 12 and week 12 adjusted least-squares (LS) means estimates at week 24 will be provided along with the corresponding standard errors and 95% confidence intervals.	• Within Arm 1 patients, difference between the fasting glucose mean changes from week 12 to week 24 and from baseline to week 12 will be provided along with its corresponding 95% confidence interval, and nominal p-value.

 
Percent change in liver fat (MRI-PDFF) from baseline to week 12
 
Percent change in liver fat (MRI-PDFF) from week 12 to week 24
 
	• For Arm 1 patients with hepatic steatosis (baseline MRI-PDFF ≥8.5%), baseline adjusted least-squares (LS) means estimates at week 12 and week 12 adjusted least-squares (LS) means estimates at week 24 will be provided along with their corresponding standard errors and 95% confidence intervals.	• Difference between the liver fat percent mean changes from week 12 to week 24 and from baseline to week 12 will be provided along with its corresponding 95% confidence interval, and nominal p-value.

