### 10.3. List of AESIs with Data Sources and Definitions of SMQ/CMQ

Table 19: Summary of AESIs and the Methods of Data Collections and Derivations

AESI	Using an e-CRF specific tick box on AE page	Using Standard MedDRA Query (SMQ)/company MedDRA Query (CMQ) or Laboratory data criteria
Hypoglycemia	Yes	Blood glucose <54 mg/dL
New onset diabetes mellitus (NODM)	Yes	For patients with no diabetes at baseline:
		• Two values of fasting (≥8 hr) plasma glucose ≥126 mg/dL (7.0 mmol) during treatment period
		OR
		• Two values of HbA1c ≥6.5% (48 mmol/mol) during treatment period
		Note: Patients who meet either of these criteria during the PBO run- in period will be considered to have diabetes at baseline.
Hyperglycemia requiring treatment	Yes	HbA1c ≥10.5% AND increase in HbA1c of ≥1.5% from baseline value OR b. Fasting glucose ≥250 mg/dL on 2 occasions AND increase in fasting glucose >50 mg/dL above baseline
Development of new or worsening of autoimmune disease	Yes	N/A
Moderate and severe Hypersensitivity reactions	Yes	CMQ 'Hypersensitivity, which is defined as Hypersensitivity SMQ (narrow) excluding the following PTs:

Protocol: R4461-PLD-20100

		0	Injection site
			dermatitis,
		0	Injection site eczema,
			Injection site
			hypersensitivity,
		0	Injections site rash,
		_	•
		0	injection site reaction,
		0	Injection site recall
			reaction,
		0	Injection site urticaria,
		0	Injection site vasculitis
Moderate and severe	Yes	N/A	
infusion reactions	105	14/11	
iniusion reactions			

^ dedicated CRF for ISR captures event PT and associated symptoms

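### The HbA1c route to diabetes at baseline needs two run-in values where one is scheduled, so unchanged pre-existing HbA1c of 6.5% or more can be counted as new-onset diabetes

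*Protocol*

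**What the plan says.** NODM is an adverse event of special interest (AESI). For patients with no diabetes at baseline, Protocol 10.1.3 gives two alternative laboratory criteria: two fasting plasma glucose values of at least 126 mg/dL, or "Two values of HbA1c ≥6.5% (48 mmol/mol) during the treatment period". It then sets the baseline rule: "Patients who meet either of these criteria during the placebo run-in period will be considered to have diabetes at baseline".

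The SAP carries this forward. Section 4.8.1.2 derives NODM from the eCRF and from laboratory data, states that "For patients with no diabetes at baseline, NODM is defined using the following lab parameters", and refers to Appendix 10.3 for the AESI definitions. Table 19 in that appendix repeats the baseline rule: "Patients who meet either of these criteria during the PBO run- in period will be considered to have diabetes at baseline".

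Protocol 8.2 sets the run-in at day -28 to day -1. In Protocol Table 1, HbA1c is marked at visit 1 (screening) and visit 4 (day -28), and not at visits 5, 6 or 7. The next HbA1c is on day 1, which Table 2 lists under the double-blind period. For glucose, Protocol 6.1 says of the run-in: "Fasting lipid and glucose levels will be collected weekly".

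The trial deliberately admits patients near the diabetes threshold. Protocol 3.2.1 says that those with fasting TG above 450 mg/dL and "with normal or mildly abnormal HbA1c (up to 7.0%) are included".

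**The concern.** The word either in the baseline rule shows that both criteria were meant to work in the run-in. The schedule leaves the HbA1c criterion one value short. A patient at 6.8% at screening, on day -28 and on day 1 has three pre-dose values at or above 6.5% and still does not meet the HbA1c rule. If HbA1c is still 6.8% at weeks 4 and 6, the same patient satisfies the NODM criterion although nothing has changed.

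At stake is the meaning of one safety count. High HbA1c is part of this disease, and the rule would turn some prevalent dysglycaemia into incident events. The SAP's early-termination changes (Section 1.2.4) reduce the efficacy analysis to descriptive summaries, but the AESI summaries of Section 5.8.2 remain planned. In a small safety set, one or two such events visibly move a percentage. No efficacy analysis or sample-size figure depends on this point.

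**Working it through.** The plan gives no figure of its own here, so the check is a count of scheduled draws followed by a probability calculation.

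**1. HbA1c draws (Protocol Tables 1 and 2)**

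| Period | HbA1c draws | Number |
|---|---|---|
| Screening | visit 1 | 1 |
| Run-in (day -28 to day -1) | visit 4, day -28 | 1 |
| Day 1, pre-dose | visit 8 | 1 |
| Double-blind, after day 1 | weeks 4, 6, 10, 12 | 4 |
| Single-blind | weeks 16, 18, 22, 24 | 4 |

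The eight on-treatment visits agree with those listed in SAP Table 6: "weeks 4, 6, 10, 12, 16, 18, 22, and 24". Two values are needed and the run-in supplies one, so the chance of meeting the HbA1c criterion there is 0 at any HbA1c level.

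**2. Chance that a stable patient is counted as NODM**

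Let m be a constant true HbA1c and s the within-patient SD. The documents give no s, so 0.1 to 0.3 percentage points is assumed, with independent draws.

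- Chance that one draw is ≥6.5%: p = 1 − Φ((6.5 − m)/s).
- Chance of at least two of n draws: P(n) = 1 − (1 − p)^n − n·p·(1 − p)^(n−1).

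Example with m = 6.8 and s = 0.2: p = Φ(1.5) = 0.933, P(4) = 0.999 and P(8) = 1.000.

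| True HbA1c | P(4), double-blind period | P(8), both periods |
|---|---|---|
| 6.5% | 0.69 | 0.965 |
| 6.6% to 7.0% | 0.85 to 1.00 | 0.995 to 1.00 |

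A patient at or above 6.5% at every draw meets the criterion at week 6, or at week 4 if the day 1 sample is treated as a treatment-period value.

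**3. The glucose route**

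Four run-in fasting glucose values are drawn (days -28, -21, -14, -7), so this criterion can be met. For a per-draw chance of ≥126 mg/dL of 0.10, 0.25, 0.50 and 0.75, the chance of at least two of four is 0.05, 0.26, 0.69 and 0.95. It therefore rescues some patients, but not reliably those whose glucose sits below or near the threshold.

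**4. How many patients**

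Protocol 11.2 expects 78% with HbA1c above 7.0%, leaving 22% × 40 = 8.8 planned patients (22% × 20 = 4.4 in cohort A) at or below it. Only those at ≥6.5%, without recorded diabetes and without the glucose trigger, are affected. The documents give none of these shares. The figure is not a strict upper bound either, because the rule has no 7.0% ceiling: a patient above 7.0% with no recorded diabetes and no glucose trigger would be caught too.

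**5. Effect of using all three pre-dose HbA1c values**

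The chance of still being counted is (1 − P(3)) × P(8). In the example, P(3) = 3p²(1 − p) + p³ = 0.987, so (1 − 0.987) × 1.000 = 0.013.

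| True HbA1c | Counted under the present rule | Counted with all pre-dose values |
|---|---|---|
| 6.5% | 0.965 | 0.48 |
| 6.6% | 0.995 to 1.00 | 0.07 to 0.31 |
| 6.8% | 1.00 | 0.00 to 0.07 |
| 7.0% | 1.00 | 0.00 to 0.01 |

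These are chances for a patient with no recorded diabetes and no glucose trigger.

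**The case against.** The best defence is that day 1 may be read as part of the run-in. The schedule footnote lets run-in scans be done up to day 1 before dosing, the day 1 HbA1c is a pre-dose sample, and SAP 10.2 accepts day 1 as baseline. On that reading there are two values and the 6.8% patient is diabetic at baseline. But the footnote covers only DXA and MRI scans, Protocol 8.2 ends the run-in at day -1, and Table 2 places day 1 in the double-blind period. An unscheduled draw could also supply a second value, since SAP 6.5 allows unscheduled measurements to determine AESIs. The statement is therefore that the criterion cannot be met on schedule, not that it could never be met.

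Second, the run-in sentence does not claim to be the only route. Diabetes is collected as medical history, and abnormal laboratory values at consent are recorded as history (Protocol 5.1, 7.2.1, 10.1.1). A patient with known diabetes controlled to 6.5% to 7.0% should fall outside NODM. This stands and narrows the affected group, although neither document ties recorded history to the NODM derivation.

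Third, Protocol 8.7 blinds investigators and sponsor to HbA1c and fasting glucose up to week 24, and laboratory AESIs are reported once the investigator confirms the value. A reader might infer a run of false 24-hour reports. The documents do not support that; the error would arise mainly in the SAP laboratory derivation.

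Fourth, a reader might infer that false events fall mostly on REGN4461, because arm 2 has 24 weeks on drug and arm 1 only 12 on placebo. That does not follow. A stable patient is counted during the double-blind period, where both arms have the same four post-day-1 draws, and SAP 5.8 summarises safety separately by period. If the drug lowers HbA1c as hypothesised, false events would if anything be fewer on drug.

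Finally, SAP 4.8.1.2 does not itself state the baseline rule, but it refers to Appendix 10.3, which does. Nothing is missing from the SAP.

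**Conclusion.** The defect stands in a limited form. As written and as scheduled, HbA1c alone cannot establish diabetes at baseline, and the SAP programs the same rule. A patient with no recorded diabetes, fewer than two run-in fasting glucose values of at least 126 mg/dL, and HbA1c already at or above 6.5% would very probably be counted as new onset if nothing changes: at least 0.995 over both periods at a stable 6.6% to 7.0%. That figure rests on an assumed within-patient SD of 0.1 to 0.3 points and independent draws. The count of one run-in draw against two required rests on no assumption beyond the stated run-in days.

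The consequence is an inflated descriptive NODM count in both arms. It is not automatic for every patient at 6.5% to 7.0%, no differential bias between arms is shown, and the number affected cannot be derived from the documents.

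**What to change.** Reconcile the baseline rule with the schedule in Protocol 10.1.3 and SAP Table 19, keeping the reference from SAP 4.8.1.2. One sentence is enough:

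> *A patient has diabetes at baseline if diabetes is recorded in the medical history, or if either two-value criterion is met by measurements taken before the first double-blind dose (HbA1c at screening, day -28 and day 1 pre-dose; all pre-dose fasting glucose values). NODM is derived only in patients without diabetes at baseline.*

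This keeps the protocol's own thresholds and two-value requirement, and fits the general definition of baseline in Protocol 11.4, which runs up to the first double-blind dose. It needs no added sample. The cost is a short edit in each document and slightly fewer patients in the NODM denominator. A patient truly at the 6.5% threshold would still be counted about half the time (0.48 under the assumptions above), which is a limit of any two-value rule at its cut-off.

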10.2. Definitions

10.2.1. Adverse Event

An AE is any untoward medical occurrence in a patient administered a study drug which may or may not have a causal relationship with the study drug. Therefore, an AE is any unfavorable and unintended sign (including abnormal laboratory finding), symptom, or disease which is temporally associated with the use of a study drug, whether or not considered related to the study drug (ICH E2A Guideline. Clinical Safety Data Management: Definitions and Standards for Expedited Reporting, Oct 1994).

10.2.2. Serious Adverse Event

An SAE is any untoward medical occurrence that at any dose:

• Results in **death** – includes all deaths, even those that appear to be completely unrelated to study drug (eg, a car accident in which a patient is a passenger).

- Is **life-threatening** in the view of the investigator, the patient is at immediate risk of death at the time of the event. This does not include an AE that had it occurred in a more severe form, might have caused death.
- Requires in-patient **hospitalization** or **prolongation of existing hospitalization**. In-patient hospitalization is defined as a hospital admission (any duration) or an emergency room visit for longer than 24 hours. Prolongation of existing hospitalization is defined as a hospital stay that is longer than was originally anticipated for the event or is prolonged due to the development of a new AE as determined by the investigator or treating physician.
- Results in persistent or significant **disability/incapacity** (substantial disruption of one's ability to conduct normal life functions).
- Is a congenital anomaly/birth defect
- Is an **important medical event** Important medical events may not be immediately life-threatening or result in death or hospitalization, but may jeopardize the patient or may require intervention to prevent one of the other serious outcomes listed above (eg, intensive treatment in an emergency room or at home for allergic bronchospasm; blood dyscrasias or convulsions that do not result in hospitalization; or development of drug dependency or drug abuse).

Criteria for reporting SAEs must be followed for these events.

10.2.3. Adverse Events of Special Interest

An adverse event of special interest (AESI; serious or non-serious) is one of scientific and medical interest specific to the sponsor's product or program, for which ongoing monitoring and rapid communication by the investigator to the sponsor can be appropriate. Such an event might warrant further investigation in order to characterize and understand it.

Adverse events of special interest for this study are detailed in Section 10.1.3.

10.2.4. Infusion Reactions

Infusion reactions are defined as any relevant AE that occurs during the infusion or within 2 hours after the infusion is completed. All infusion reactions must be reported as AEs (defined in Section 10.2.1) and graded using the grading scales as instructed in Section 10.3.1.

